#### 6.2.2 Explanation for why the research could not practicably be conducted without access to and use of PHI

The medical record will be reviewed during the clinic visit to determine eligibility.

#### 6.2.3 Explanation for why the research could not practicably be conducted without the waiver or alteration of authorization

Waiver to view the medical record is necessary to determine eligibility.

### 6.3 Waiver or alteration of authorization statements of agreement

Protected health information obtained as part of this research will not be reused or disclosed to any other person or entity, except as required by law, for authorized oversight of the research study, or for other permitted uses and disclosures according to federal regulations.

The research team will collect only information essential to the study and in accord with the 'Minimum Necessary' standard (information reasonably necessary to accomplish the objectives of the research) per federal regulations.

Access to the information will be limited, to the greatest extent possible, within the research team. All disclosures or releases of identifiable information granted under this waiver will be accounted for and documented.

## 7.0 Study Design and Procedures

### 7.1 Study Design

[figure not shown]
Thirty patients will be identified in the clinic with indications for open or arthroscopic shoulder surgery. Patients will be informed about the current prospective study and written consent will be obtained. Both shoulders of each patient will be included for the study; the surgical side shoulder will serve as a “Treatment shoulder” while the normal non-operative contralateral shoulder will serve as a “Control shoulder”. All patients will receive a wireless, low-level microcurrent-generating antimicrobial dressing (JumpStart® Antimicrobial Wound Dressing, Arthrex, Inc., Naples, Florida, USA) (Figure 1) and hydrogel on the posterior aspect of their Treatment shoulder 2 days prior to their surgery. A small amount of hydrogel will be applied to the undersurface of JumpStart dressing. The adhesive dressing will make the JumpStart stick to the skin. The dressing will be kept on the shoulder until the time the patient is transferred to the operating room on the day of surgery. The dressing will be applied by a member of the research team at clinic. Upon transfer to the operating room on the day of surgery, the JumpStart dressing will be removed from the Treatment shoulder. All patients will receive routine preoperative IV antibiotics (either Cefazolin or Clindamycin) at least 5 minutes prior to skin incision and a routine operative skin preparation for both shoulders using standard, alcohol-based preparation (ChloraPrep, 2% chlorhexidine gluconate and 70% isopropyl alcohol; Enturia, El Paso, TX, USA) immediately before skin incision in the operating room.

At the time of the surgery, 2 separate 3-mm punch biopsy specimens will be taken from the posterior shoulder skin of both shoulders using a disposable biopsy punch (Disposable Biopsy Punch; Robbins Instruments, Chatham, NJ, USA) (Figure 2) . The biopsy sites will be closed with an adhesive tape (Steri-Strip, 3M, Maplewood, MN, USA) and covered with a routine gauze dressing. Samples will be transferred directly into separate sterile specimen containers from the biopsy punches using clean, sterile forceps. Specimens will then be transferred directly to a single laboratory for culture. Anaerobic and aerobic culture substrates will be used and held for 14 days for *P. acnes* only, given literature that shows *P. acnes* can grow on either substrate. Anaerobic culture plates will be incubated for 4 days and broth cultures for 14 days before concluding that the final report is negative. To serve as a “negative control,” while wearing sterile gloves, in the first 20 patients, a sterile culture swab will be opened in the operating room, wiped through the air, and sealed in a specimen container. Chocolate plate will serve as a settle plate in the OR suite for 10 minutes and incubated for 4 days. Data will include demographic data of patients, positive culture rates, and the number of days before resulting in positive culture. All culture results will be reviewed and the patient will be marked positive if any of the cultures were positive. Patients will be scheduled for postoperative, routine follow-up visits. The rest of patient care will follow our current routine standard care without any modifications or interventions.

## JUMPSTART® ANTIMICROBIAL WOUND DRESSING

**JumpStart**  
ADVANCED MICROCURRENT TECHNOLOGY®

### New Knee Dressing

#### Bioelectric Technology

#### High-Performance Adhesive

- Stretchable for enhanced mobility
- Water-resistant
- Designed for multiday wear time

#### Fit Flaps

- Adapt to patellar contours
- Seal and protect

#### Bend Reliefs

- Maximizes range of motion
- Minimizes potential for shear force

#### Side Contours

- Universal fit to diverse anatomy
- Minimize wrinkling

#### Shin Contour

- Gapfree fit

**Shorter** overall dressing length for improved fit and mobility.

### New Energel™ Wound Hydrogel

- Compatible with JumpStart antimicrobial wound dressing
- Maintains JumpStart wound dressing's electric field for 5- to 7-day wear time
- Creates a moist wound environment
- Double packaged sterile sachet for use in operating room
- Nonwasteful 7.5 g sachet for true single use
- Available in a box of 10 sachets

## 7.2 Study Procedures

### 7.2.1 Pre-operation

Patient will be seen in the outpatient clinic during their standard of care 1 week pre-operation visit. Patient will be provided information about the study, consented, and recruited to the study. Following the consent, patients will have a research visit scheduled 2 days before surgery to have the JumpStart dressing material applied to their operative shoulder by a member of the research team. The JumpStart dressing will be kept until the day of surgery. Excessive hair will be removed from the dressing site at the time of dressing application to ensure a secure dressing attachment. All patients will receive standard of care pre-operation routine skin care instructions during the visit as all patients receive having this type of surgery.

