### 7.4.2 Treatment Regimen

The dressings will be applied over the posterior aspect of the shoulder above the posterior axilla.

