### 7.4.4 Subject Compliance Monitoring

### 7.4.5 Blinding of the Test Article

N/A

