**8.2 Sample size determination**

A priori sample size calculation was performed using some of the previously published data. Assumptions were made as follows: the primary outcome measure was the intraoperative culture results (e.g. positive, negative) for *P. acnes* by evaluating bacterial cultures from two skin biopsies obtained from the posterior aspect of the shoulder at the time of the surgery. Based on a previous study, the positive culture rate in untreated shoulders was set at 60%. We set the minimally clinically significant difference (MCID) of positive culture rate at 30% (a half of 60%) as a previous study described. Using a two-tailed McNemar test for two dependent groups with a power of 0.8 and an alpha of 0.05, the priori sample size calculation suggested a total of 30 patients for the study.

Probability		Treatment shoulder		
		Positive culture	Negative culture	
Control shoulder	Positive culture	0.25	0.35	0.6
	Negative culture	0.05	0.35	0.4
		0.3	0.7	1

Exact - Proportions: Inequality, two dependent groups (McNemar)

Options:  $\alpha$  balancing:  $\alpha/2$  on each side, approximation

Analysis: A priori: Compute required sample size

Input: Tail(s) = Two

Odds ratio = 7

$\alpha$  err prob = 0.05

Power (1- $\beta$  err prob) = 0.8

Prop discordant pairs = 0.4

Output: Lower critical N = 2.000000

Upper critical N = 10.000000

Total sample size	=	30
Actual power	=	0.8180007
Actual $\alpha$	=	0.0385742
Proportion p12	=	0.3500000
Proportion p21	=	0.0500000

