### 8.3 Statistical methods

If at least one of the two cultures from a shoulder turns positive, that shoulder will be counted as a “positive culture” shoulder. The results of the two cultures from each shoulder will be McNemar test will be used to compare the proportions of positive culture rates between paired shoulders. Ordinal or interval Demographic data will be compared between the two groups using parametric vs nonparametric tests depending on their normality. Nominal data will be compared using Fisher’s exact test or contingency table. The negative control data will be analyzed in comparison to the results of the treatment and normal control shoulders.

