## 9.0 Confidentiality, Privacy and Data Management

See the Research Data Plan Review Form.

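### Hair is removed only on the dressed shoulder, and no masked reading of cultures by side is described: two probably small threats to attribution that are cheap to remove

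*Combined protocol and SAP*

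**What the plan says.** **Hair.** Section 7.2.1 schedules a research visit 2 days before surgery at which the dressing is put on the operative shoulder, and adds: "Excessive hair will be removed from the dressing site at the time of dressing application to ensure a secure dressing attachment". Section 7.4.2 gives the location: "The dressings will be applied over the posterior aspect of the shoulder above the posterior axilla". Section 7.1 gives the sampling site: "2 separate 3-mm punch biopsy specimens will be taken from the posterior shoulder skin of both shoulders". Section 7.4.1 says that the control shoulder does not receive the dressing. The only skin preparation written for both shoulders is the alcohol-based one applied in the operating room (7.1, 7.4.1).

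**Assessment.** Section 7.1 puts the biopsies in separate sterile containers and continues: "Specimens will then be transferred directly to a single laboratory for culture". It then has the culture results reviewed and the number of days to a positive culture recorded. It does not say how containers are labelled or whether the reader knows the side. Section 7.4.5, headed "Blinding of the Test Article", is answered N/A, while 19.6 describes a situation in which the patient is unblinded. Section 9.0 says only: "See the Research Data Plan Review Form". That form is not among the documents.

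**Analysis.** Section 8.3: "McNemar test will be used to compare the proportions of positive culture rates between paired shoulders".

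**The concern.** The objective in 1.1 is the efficacy of the dressing. Pairing removes whatever a patient's two shoulders share. It does not remove anything that always falls on the treated side, and because the treated side is always the operative one, chance does not balance such differences. Hair removal at the site later cultured is one of them, and it is avoidable.

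Reading the cultures is a different matter. As written, both shoulders' specimens are handled alike, so missing codes do not make the shoulders differ. They leave open that whoever calls a culture positive, or dates its conversion, knows which shoulder was dressed. With few discordant pairs expected, a single call can decide the primary test.

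**Working it through.** **1. The two shoulders side by side**

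| Step | Treatment shoulder | Control shoulder | Section |
|---|---|---|---|
| Hair removal 2 days before surgery | Where excessive, at dressing site | None written | 7.2.1 |
| Hydrogel, dressing and adhesive cover | Yes | No | 7.1, 7.4.1 |
| Operative side | Always | Never | 7.1 |
| Alcohol-based skin preparation | Yes | Yes | 7.1, 7.4.1 |
| Two punch biopsies, posterior skin | Yes | Yes | 7.1 |
| Separate containers, one laboratory, fixed incubation | Yes | Yes | 7.1 |

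The first three rows move with treatment. The second is the intervention, the third is a disclosed design choice, and only the first is incidental. The last row is the same on both sides, which is why the coding question concerns who reads the cultures.

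**2. What the paired test estimates**

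McNemar's test compares p12 (control positive, treated negative) with p21 (the reverse). Their difference is the control positive rate minus the treated positive rate. In a simple additive form,

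p12 − p21 = D + f × H + (other side-linked effects),

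where D is the reduction due to the dressing, f the share of patients who have hair removed, and H the reduction in positive rate that hair removal causes in them (H may be negative or zero). Only the sum can be estimated. The documents give neither f nor H, and the plan does not ask for f to be recorded.

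**3. The plan's own figure**

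Inputs from 8.2: 30 pairs, discordant proportion 0.40, p12 = 0.35, p21 = 0.05, α/2 in each tail.

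- Discordant pairs: 0.40 × 30 = 12.
- Lower tail with no effect: P(X ≤ 2) = (1 + 12 + 66)/4096 = 0.0193, below 0.025. P(X ≤ 3) = 299/4096 = 0.073, above it. So the critical values are 2 and 10, and 8.2 prints "Upper critical N = 10.000000".
- Actual α: 2 × 79/4096 = 0.0386, as printed.
- Power: with q = 0.35/0.40 = 0.875, P(X ≥ 10) = 0.2713 + 0.3453 + 0.2014 = 0.818, as printed.

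**4. One reclassified shoulder, starting from 10 v 2**

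The p-values are exact two-sided binomial. A change in a discordant pair makes it concordant. A change in a concordant pair makes it discordant, in one direction or the other. That gives four outcomes:

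| Split | Calculation | p |
|---|---|---|
| 10 v 2 (start) | 2 × 79/4096 | 0.039 |
| 9 v 2 | 2 × (1 + 11 + 55)/2048 | 0.065 |
| 10 v 3 | 2 × (1 + 13 + 78 + 286)/8192 | 0.092 |
| 10 v 1 | 2 × (1 + 11)/2048 | 0.012 |
| 11 v 2 | 2 × (1 + 13 + 78)/8192 | 0.022 |

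Two of the four lose significance and two keep it. This shows how finely the result can be balanced. It does not show that any culture will be misread.

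**The case against.** **Hair removal is part of applying the dressing.** Its stated purpose is attachment, so the contrast could be read as the dressing as applied, which is a legitimate comparison. This stands as a possible reading, but 7.4.1 describes the test article without it. If that is the intention, the plan should say so and record who had it.

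**Culture growth is fairly objective.** Incubation periods are fixed in 7.1, and nothing in the documents suggests a route to misreading. N/A under 7.4.5 answers a question about a visible dressing and does not address the laboratory. Coding may also be set out in the form cited in 9.0. All of this stands and keeps the risk small. A reader might infer that specimens are certainly uncoded, but the documents show only that coding is not described in them.

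**The size is unknown.** A reader might infer that hair removal inflates the apparent effect or costs substantial power. The documents support neither. They give no direction; hair removal concerns only some patients; and 2.1 places the organism under the epidermis, in sebaceous glands. The only randomised decolonisation comparison described there, 7 days of oral doxycycline, gave 22/37 v 16/37 with a positive culture (59% v 43%, 16 points) and is reported as not significant. Nothing suggests that hair removal comes near that, so tables of assumed shifts would be speculation.

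**The fixes do not isolate the dressing.** This is correct. Hydrogel, two days of adhesive cover and operative side still coincide with treatment. A reader might go further and call the fixed operative-side allocation an error, but 7.1 discloses it as a design choice. It limits interpretation.

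**Matching hair removal has a price.** It adds a research-only procedure to the healthy shoulder, and 8.2 takes its 60% control rate from untreated shoulders. This stands, and it is a reason to offer the alternative of defining and recording hair removal.

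**Conclusion.** The point holds in a limited form, as two separate matters. First, hair removal written only for the dressed site is a side-linked difference in some patients that the McNemar test cannot separate from the dressing. This assumes that the biopsies come from the skin that was dressed, which the shared posterior location implies, and that the control side gets no unwritten matching step. Second, no masking of side is described for those who classify cultures and days to positivity, so assessment may be unmasked.

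Neither bias has a size or direction in the documents, and both are probably small. The one relevant figure is the sensitivity near the cut-off. With 12 discordant pairs, as 8.2 assumes, a 10 v 2 result can lose significance when one shoulder is reclassified, and can equally keep it. The actual number of discordant pairs will vary. The changes are worth making because they cost little and cannot be made once the cultures have been read.

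**What to change.** 1. **Masking (7.1 and 7.4.5).** State that containers carry study codes and that the laboratory and the person classifying cultures and days to positivity do not know side or treatment. If the Research Data Plan Review Form already provides for this, cite it. Cost: a code list held by an existing team member who does not classify cultures.
2. **Hair (7.2.1).** Either state that, when hair is removed at the dressing site, the matching posterior site on the control shoulder is treated in the same way at the same visit, or define hair removal as part of the intervention in 7.4.1. In both cases record in which patients it was done. Cost of matching: a few minutes at an existing visit and minor hair removal on the other shoulder in some patients, mentioned in the consent form. Cost of defining: wording and one data field.
3. **Interpretation.** Describe the result as the effect of the dressing as applied, with hydrogel and cover, on the operative shoulder.
4. **Consistency.** Reconcile N/A in 7.4.5 with the unblinding text in 19.6. This does not bear on attribution.

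No extra patients, visits or biopsies are needed.

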### 7.2.2 Post-operation

Patients will follow our current routine standard care follow-up protocol for each surgical procedure. The biopsy sites will be carefully examined by the PI or his patient care team to ensure proper healing upon each postoperative return visit. The first postoperative visit is at 2 weeks after surgery. Any wound problems such as bleeding, drainage, abnormally increased pain, feeling of local warmth, erythema, and abnormal swelling will be immediately reported to the PI or his patient care team. The duration of the post-operation routine care follow-up can take place between a few weeks to several months depending on the procedure. The culture results will be obtained within 14 days post-operation. Any change in the condition of the biopsied area will be recorded and followed, including infections, as part of the routine care visits.

## 7.3 Duration of Participation

Patients will be involved in this study only during the time of their shoulder surgery, which include pre-operation consent and post-operation routine follow-up. Pre-operation consent will mark the beginning of the patients' participation and will take place approximately 1 week before the surgery. The patients will use the dressing only during this pre-operation period. The pre-operative visit will take approximately 30 minutes. Application of the dressing in clinic will take approximately 30 minutes. The skin biopsies in the operating room will take about 5 minutes to obtain. The duration of the post-operation routine care follow-up can take place between a few weeks to several months depending on the procedure. The culture results will be obtained within 14 days post-operation. Any change in the condition of the biopsied area will be recorded and followed, including infections, as part of the routine care visits.

## 7.4 Test Article(s) (Study Drug(s) and/or Study Device(s))

### 7.4.1 Description

In each patient, the Treatment shoulder will receive preoperative applications of a wireless, low-level microcurrent-generating antimicrobial device (JumpStart® Antimicrobial Wound Dressing, Arthrex, Inc., Naples, Florida, USA) 2 days prior to their surgery. The control will not receive this treatment. On the day of surgery, in the operating room, both shoulders will receive preoperative applications of standard, alcohol-based preparation (ChloraPrep, 2% chlorhexidine gluconate and 70% isopropyl alcohol; Enturia, El Paso, TX, USA) immediately before the surgery. JumpStart is a broad-spectrum antimicrobial wound dressing featuring Advanced Microcurrent Technology™. Embedded in the dressing are microcell batteries made of elemental silver and zinc applied in a dot-matrix pattern to a polyester substrate. In the presence of a conductive medium such as wound exudate, water-based hydrogels or saline, microcurrents are generated at the dressing surface, due to its inherent design.

### 7.4.2 Treatment Regimen

The dressings will be applied over the posterior aspect of the shoulder above the posterior axilla.

### 7.4.3 Method for Assigning Subject to Treatment Groups

NA

### 7.4.4 Subject Compliance Monitoring

### 7.4.5 Blinding of the Test Article

N/A

### 7.4.6 Receiving, Storage, Dispensing and Return

#### 7.4.6.1 Receipt of Test Article

All of the standard-of-care alcohol-based prep, iodine-barrier drapes are already available both at the main operating rooms and HOSC operating rooms. The alcohol-based prep and iodine-barrier drapes have been routinely used for shoulder cases in the main operating rooms and HOSC operating rooms. The JumpStart dressing has been used in standard of care, select cases for immediate postoperative dressing and is available in the main operating room.

For this study, we will purchase JumpStart dressings from the vendor (Arthrex, Naples, FL) using the PI's personal research fund. Each package will contain 8" x 8" Antimicrobial Wound Dressing that can be cut to fit surgical sites and shape conforms easily to body contours for patient comfort.

#### 7.4.6.2 Storage

The dressing will be stored in dry conditions at controlled room temperature, protected from light. Controlled room temperature is 20°C to 25°C (68°F to 77°F). Excursions are permitted between 15°C and 30°C (59°F and 86°F). Brief exposure to temperatures up to 40°C (104°F) may be tolerated provided the mean kinetic temperature does not exceed 25°C (77°F); however, such exposure will be minimized.

Dressing will be stored in a locked office [name] in a locked metal cabinet, separated from other clinical supplies, in the Clinical Research

Office. The room is temperature controlled, and its temperature will be monitored via the thermostat and recorded on a temperature log daily.

**7.4.6.3 Preparation and Dispensing**

The application of the dressings will be prepared and administered by an investigator on the study team in clinic from the research supply. The dressing will be disposed according to local environmental procedures.

**7.4.6.4 Return or Destruction of the Test Article**

N/A

**7.4.6.5 Prior and Concomitant Therapy**

The dressing cannot be applied in conjunction with topical agents such as antimicrobial ointments, enzymatic debriders, antibiotic creams or ointments, silver- or zinc-containing creams, oxidizing agents, or petroleum-based products. The dressing must be removed during energy-based procedures (e.g. radiofrequencies, ultrasound, or radiation) where the dressing may interfere with delivery.

## 8.0 Subject Numbers and Statistical Plan

**8.1 Number of Subjects**

Thirty patients will be recruited for this study.

**8.2 Sample size determination**

A priori sample size calculation was performed using some of the previously published data. Assumptions were made as follows: the primary outcome measure was the intraoperative culture results (e.g. positive, negative) for *P. acnes* by evaluating bacterial cultures from two skin biopsies obtained from the posterior aspect of the shoulder at the time of the surgery. Based on a previous study, the positive culture rate in untreated shoulders was set at 60%. We set the minimally clinically significant difference (MCID) of positive culture rate at 30% (a half of 60%) as a previous study described. Using a two-tailed McNemar test for two dependent groups with a power of 0.8 and an alpha of 0.05, the priori sample size calculation suggested a total of 30 patients for the study.

Probability		Treatment shoulder		
		Positive culture	Negative culture	
Control shoulder	Positive culture	0.25	0.35	0.6
	Negative culture	0.05	0.35	0.4
		0.3	0.7	1

Exact - Proportions: Inequality, two dependent groups (McNemar)

Options:  $\alpha$  balancing:  $\alpha/2$  on each side, approximation

Analysis: A priori: Compute required sample size

Input: Tail(s) = Two

Odds ratio = 7

$\alpha$  err prob = 0.05

Power (1- $\beta$  err prob) = 0.8

Prop discordant pairs = 0.4

Output: Lower critical N = 2.000000

Upper critical N = 10.000000

Total sample size	=	30
Actual power	=	0.8180007
Actual $\alpha$	=	0.0385742
Proportion p12	=	0.3500000
Proportion p21	=	0.0500000

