### 10.7 Statistical tests

The proportion of positive cultures will be determined using Fisher’s exact test to compare the positive culture rates. Ordinal or interval Demographic data will be compared between the two groups using parametric vs nonparametric tests depending on their normality. Nominal data will be compared using Fisher’s exact test or contingency table.

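### The stated power for 30 patients (0.818) holds only with exactly 12 discordant pairs; averaged over the discordant count it is 71% to 79%, depending on a McNemar version that 8.3 does not name

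*Combined protocol and SAP*

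**What the plan says.** Section 8.1 fixes the number of patients: "Thirty patients will be recruited for this study". Each patient contributes one treated and one control shoulder.

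Section 8.2 states that "the positive culture rate in untreated shoulders was set at 60" per cent and takes a 30-point reduction as the difference to detect. Its table gives 0.35 for control-positive/treatment-negative pairs and 0.05 for the reverse, so 0.40 of pairs are discordant, with an odds ratio of 7. The calculation is described as "Using a two-tailed McNemar test for two dependent groups with a power of 0.8 and an alpha of 0.05". The software heading reads "Exact - Proportions: Inequality, two dependent groups (McNemar", and the options line ends "on each side, approximation". The output gives critical values 2 and 10, a total of 30, actual power 0.8180007 and actual alpha 0.0385742.

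For the analysis, section 8.3 says that "McNemar test will be used to compare the proportions of positive culture rates between paired shoulders", with no version given. Section 10.7 says: "The proportion of positive cultures will be determined using Fisher’s exact test to compare the positive culture rates".

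**The concern.** A McNemar test uses only the discordant pairs. Critical values of 2 and 10 belong to one particular discordant count, so the printed power appears to describe a trial in which that count is known in advance. The trial fixes patients, not discordant pairs. With about a dozen informative pairs the test is very discrete, and its power jumps as the count changes. One favourable count can then misstate the power of the design.

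The chance of missing the planned effect would be larger than 8.2 implies. How much larger depends on which McNemar version is run, and that is left open. The protocol has one primary outcome and no secondary endpoints, so an unnamed version leaves room for a choice after the data are seen.

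**Working it through.** **Inputs (section 8.2 unless noted).** N = 30 (8.1); p12 = 0.35; p21 = 0.05; discordant proportion 0.35 + 0.05 = 0.40; two-sided alpha 0.05. Given a discordant pair, the chance that it favours treatment is 0.35/0.40 = 0.875.

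**Step 1: reproduce the printed output.** Set the discordant count at D = 30 × 0.4 = 12 and reject if the number favouring treatment, X, is ≤ 2 or ≥ 10.

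- Alpha: 2 × (1 + 12 + 66)/4096 = 0.0385742.
- Power: P(X ≤ 2 or X ≥ 10), X ~ Bin(12, 0.875), = 0.8180007.

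Both agree with 8.2 to seven decimals. The printed power is therefore the power conditional on D = 12.

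**Step 2: distribution of the discordant count.** With 30 patients, D ~ Bin(30, 0.4): P(D < 12) = 0.431, P(D = 12) = 0.147, P(D > 12) = 0.422.

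**Step 3: exact-test power by count.**

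| D | 9 | 10 | 11 | 12 | 13 | 14 | 15 |
|---|---|---|---|---|---|---|---|
| Power | 0.69 | 0.64 | 0.59 | 0.82 | 0.78 | 0.75 | 0.89 |

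Power jumps between 11 and 12, so the single case used in 8.2 sits just above a step.

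**Step 4: average over D.** Power = Σ P(D = d) × P(reject | d), with X ~ Bin(d, 0.875) and rejection when the two-sided p ≤ 0.05.

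| Version | Power, N = 30 | Chance of missing the effect | Size at 0.4 discordance |
|---|---|---|---|
| Exact | 71.3% | 28.7% | 2.4% |
| Continuity-corrected | 71.0% | 29.0% | 2.3% |
| Mid-p | 79.4% | 20.6% | 4.3% |
| Uncorrected chi-square | 79.5% | 20.5% | 4.3% |

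The chance of missing the effect is 18.2% as printed and 20% as targeted. Over all discordant proportions at N = 30, the maximum size is 4.9% for mid-p and 5.4% for the uncorrected test. Power of 80% is first reached at 31 evaluable pairs with mid-p (80.9%) and at 36 with the exact test (81.3%; 35 pairs give 79.9%).

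**Step 5: can the version change the result?** Take 11 discordant pairs split 9 to 2.

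- Exact: 2 × (1 + 11 + 55)/2048 = 0.0654.
- Mid-p: 0.0654 − 55/2048 = 0.0386.
- Uncorrected: (9 − 2)²/11 = 49/11 = 4.45, p = 0.035.
- Continuity-corrected: (7 − 1)²/11 = 36/11 = 3.27, p = 0.070.

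The mid-p value never exceeds the exact one. Under the plan's table the two therefore disagree with probability 0.7939 − 0.7131 = 0.081.

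**Step 6: Fisher's test as in 10.7.** Full enumeration of the four cells (0.25, 0.35, 0.05, 0.35) at N = 30, analysed as 30 against 30 unpaired shoulders, gives 56.9% power, a 43% chance of missing the effect.

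**Step 7: sensitivity to p21, same 30-point difference.**

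| p21 | Exact | Mid-p |
|---|---|---|
| 0.02 | 82.8% | 89.6% |
| 0.03 | 78.7% | 86.0% |
| 0.05 (plan) | 71.3% | 79.4% |
| 0.10 | 58.6% | 67.3% |
| 0.12 (shoulders independent: 0.4 × 0.3) | 55.1% | 63.5% |

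**The case against.** The strongest reply is that nothing was miscalculated. The output is internally correct, and 8.2 prints the option used. That is true: the figure is conditional, not a slip. But 8.2 presents it as the power of a 30-patient study, and it is not that.

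A second reply is that the software heading already names the exact test, so the version is settled and the other versions come from outside the documents. That is a fair reading of 8.2. However, a heading in a sample-size output does not commit the analysis in 8.3 to that version, and on this reading power is 71%, the larger shortfall.

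Third, with mid-p or the uncorrected test the gap is about half a point, or one patient, which is trivial beside the uncertainty in p21 = 0.05, for which 8.2 gives no specific source. This stands: only the shortfall with the exact or continuity-corrected test is material, and p21 moves power more than the averaging does. It is a reason to name the version and show the sensitivity, not to keep 0.818.

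Fourth, the 9-to-2 split is a chosen example. At 9, 10, 12, 13 and 15 discordant pairs exact and mid-p have the same power; they part at 8, 11, 14 and 16. The 8% overall disagreement already allows for this.

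Finally, the Fisher conflict between 8.3 and 10.7 is a distinct defect, and 10.7 sits in the data and safety monitoring section. That is so, but both sections address the same comparison, so the test cannot be settled in 8.3 without also correcting 10.7.

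**Conclusion.** The concern holds. Under the plan's own table, with all 30 pairs evaluable and two-sided alpha 0.05, none of the four usual McNemar versions delivers the stated 0.80. The shortfall from target is about 9 points for the exact and continuity-corrected tests and about half a point for mid-p and uncorrected. Against the printed 0.818 the gaps are about 10 to 11 points and about 2 points. The documents do not settle which version applies, and 10.7 names an unpaired test that was not powered.

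The result rests on p12 = 0.35 and p21 = 0.05. A smaller p21 would lift even the exact test above 80% (82.8% at 0.02), and a larger one would lower every version. Lost cultures or withdrawals would reduce power further, and 8.1 and 8.2 make no allowance for them. The design is not invalidated. The power statement and the choice of primary test should be corrected.

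**What to change.** Name one McNemar version and use it in all three places.

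- **8.3:** state that the primary comparison is the two-sided mid-p McNemar test at alpha 0.05. Mid-p stays within 5% at N = 30 (maximum size 4.9%), which the uncorrected test does not.
- **8.2:** replace the power statement with one for that test: with 30 evaluable pairs, p12 = 0.35 and p21 = 0.05, power is 79%, averaged over the number of discordant pairs. If the team prefers the exact test, name it in 8.3 and state 71% here.
- **10.7:** replace Fisher's exact test for the positive culture rates with the test named in 8.3.

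If sensitivity to p21 is shown, give values on both sides of 0.05.

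The cost is one sentence in each section, with no added patients or procedures, and a less favourable stated power. Should the team wish to meet the 80% target instead, the figures are 31 evaluable pairs with mid-p or 36 with the exact test, before any allowance for losses.
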